Novel use of an enhanced fluoroscopic imaging device to reduce radiation exposure and operative time during intramedullary nailing of hip fractures

NCT02856828

Purpose of the Study:

To evaluate the effectiveness of a novel digital image enhancement (DIE) technology called LessRay in reducing the radiation exposure to both the patient and surgical staff during standard intramedullary nail placement for treatment of hip fractures. Secondarily, to evaluate whether the image quality and reproducibility of desired images can be improved with use of the LessRay Device. Finally, to evaluate whether LessRay Device reduces total operative time.

Background & Significance:

Intraoperative exposure to ionizing radiation is a growing concern for the safety of both patient and OR staff[1-12]. Several studies have shown an association between the dose of radiation the surgeon/surgical staff is exposed to and several types of cancers, including thyroid cancer[1, 3, 6, 7]. Efforts to reduce the amount of radiation during fluoroscopic procedures often result in decreased image quality (i.e. “low pulse rate” imaging). LessRay Device is able to digitally enhance images obtained from a C-arm machine using a low-dose pulse setting allowing for reduction in radiation dose while maintaining image quality. Moreover, LessRay Device allows for saving the precise location of the C-arm in space when the desired image is obtained. This allows for easy return to the exact spot where a previous image was taken, rather than taking multiple fluoroscopic images to return to the similar image. This theoretically reduces both the radiation exposure and total operative time. It also aids in evaluating and confirming reductions throughout the case as the surgeon can return to the previously obtained “perfect” or preferred AP/lateral/oblique image precisely.

The DIE system is a standalone computer display system interfaced to a fluoroscope with a video cable and combines the current image with a prior baseline image of the same anatomy. An algorithm provides for digitally enhanced images (higher resolution) using the low dose-pulse setting.

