We anticipate that our results will show the LessRay Device provides a way to drastically reduce the amount of radiation exposure to both the patient and surgical staff during routine intertrochanteric hip fracture fixation. Further studies could then be performed in the hopes of reducing radiation exposure during other orthopaedic trauma cases as well.

We are also hopeful that utilizing the “saved” image feature of the technology will significantly reduce overall operative time while not compromising image quality.

Design & Procedures:

This will be a prospective, randomized study. Patients presenting with closed, intertrochanteric hip fractures requiring intramedullary nail placement will be enrolled. Inclusion criteria will include adult, non-pregnant patients. Patient demographics (age, sex, BMI, any previous hip surgery), fracture type, and total radiation dose to the primary and assistant surgeon, as well as surgical tech and the patient will be documented. Primary surgeon characteristics will also be collected, i.e. post-graduate year (PGY), in

order to account for any differences in training level leading to increased OR time and/or radiation usage.

[figure not shown]
Total radiation emission as documented by the C-arm machine will be recorded. The exact radiation dose to the patient, primary and assistant surgeons, and surgical technician will also be monitored with individual dosimeter badges. Total operative time will be documented. Finally, a brief survey will be issued to the primary and assistant surgeons asking the question: "Was the image quality 'poor,' 'satisfactory,' or 'superior.'" They will also be asked to rate the image quality on a scale of 1-10. Responses to these questions for the standard of care (SOC) fluoroscopy vs. DIE will be compared.

All adult patients presenting with a closed intertrochanteric hip fracture requiring intramedullary nailing will be screened for enrollment. The only exclusion criteria for the study will be age <18 years.

Selection of Subjects:

All adult patients presenting with a closed hip fracture requiring intramedullary nailing. The only exclusion criteria for the study will be age <18 years. Consented subjects will be randomized to either standard of care (SOC) fluoroscopy use or the DIE.

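### The survey's top image-quality answer, 'superior', has no stated comparator and comes from operating surgeons with no masking described, so it may be read differently in the two arms

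*Combined protocol and SAP*

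**What the plan says.** All references are to the combined protocol and SAP.

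- **Aim (Purpose of the Study).** Image quality is a named secondary purpose: "Secondarily, to evaluate whether the image quality and reproducibility of desired images can be improved with use of the LessRay Device".
- **Raters (Design & Procedures).** "a brief survey will be issued to the primary and assistant surgeons". These are the surgeons who did the case, in both arms.
- **First item (Design & Procedures).** The survey is described as "asking the question: 'Was the image quality 'poor,' 'satisfactory,' or 'superior". No category is defined and no reference for the third is named.
- **Second item (Design & Procedures).** "They will also be asked to rate the image quality on a scale of 1-10". The ends of the scale carry no labels.
- **Comparison (Design & Procedures).** "Responses to these questions for the standard of care (SOC) fluoroscopy vs. DIE will be compared".
- **Visibility of the arm (Background & Significance).** "The DIE system is a standalone computer display system interfaced to a fluoroscope with a video cable". Study Interventions adds that the device is attached to the regular C-arm. Neither masking of the surgeons nor independent image reading is described.
- **Expectation (Background & Significance).** The device is presented as "allowing for reduction in radiation dose while maintaining image quality", and the hope for the saved-image feature is that it will "significantly reduce overall operative time while not compromising image quality".
- **Test (Data Analysis & Statistical Considerations).** Percentages are compared by chi-square, or by Fisher's exact test when expected counts fall below 5, with p<0.05 called significant.

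**The concern.** 'Poor' and 'satisfactory' grade the images on their own. 'Superior' invites the question: superior to what?

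In a LessRay case there is a ready answer, namely the usual fluoroscopy that the device is meant to improve on. In an SOC case the images are the usual fluoroscopy, so some surgeons may treat 'satisfactory' as the practical top of the scale. If so, the two arms are scored on different effective ranges and the scores are then compared as if the ranges were the same. Randomisation balances patients; it does not correct a measurement difference that follows the arm.

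At stake is the secondary image-quality aim. The two survey items are the only image-quality measures that the plan describes. An apparent gain on the first could arise partly from how its top label is worded, and an answer recorded under an ambiguous label cannot be reinterpreted at analysis.

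**Working it through.** **1. The plan's own figure.** The only sample-size figure concerns radiation dose, not the survey. I reproduced it to confirm that it is sound and separate from this point.

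- Inputs (sample-size paragraph under Selection of Subjects): n = 25 per group, difference 500, SDs 650 and 240, two-sided alpha 0.05, unequal-variance t-test.
- Standard error = sqrt(650²/25 + 240²/25) = sqrt(16,900 + 2,304) = 138.6.
- Noncentrality = 500/138.6 = 3.61; Satterthwaite df = 30.4.
- Power from the noncentral t = 93.7%, as stated. For a difference of 400 it is 79.8%, against the stated approximate 80%.

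Nothing in the survey wording touches this calculation.

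**2. The two survey items side by side.**

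| | Three-category item | 1-10 rating |
|---|---|---|
| Comparative wording | Yes, in the top category | No |
| Reference or definitions given | None | None; ends unlabelled |
| Rater | Operating surgeons, both arms | The same |
| Masking described | None | None |
| Compared between arms | Yes | Yes |

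The wording problem belongs to the first item only. Missing anchors and missing masking apply to both. The plan does not say which item takes precedence if they disagree.

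**3. How much a tilt would matter.** The documents give no survey response rates, so this step is an illustration on assumed shares. Assumptions: images are truly equal; 25 ratings per arm, one per case (the plan has two raters per case and does not say how their answers are combined); 'superior' against the other two answers pooled. For every pair of counts (a in SOC, b in LessRay) I applied the plan's rule: Fisher's exact test if the smallest expected count is below 5, otherwise chi-square without continuity correction. I then summed Binomial(25, p_SOC) × Binomial(25, p_LessRay) over the pairs with p<0.05 and b > a.

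| Assumed 'superior' share in SOC | No tilt | +10 points in LessRay | +20 points | +30 points |
|---|---|---|---|---|
| 10% | 0.5% | 11% | 41% | 72% |
| 20% | 2% | 13% | 35% | 64% |
| 40% | 3% | 13% | 34% | 62% |

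Each entry is the chance of a significant result favouring LessRay when the images do not differ.

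As expected counts from the 10% base: 25 × 0.10 = 2.5 'superior' ratings in SOC, against 25 × 0.20 = 5 (a 10-point gap) or 25 × 0.40 = 10 (a 30-point gap) in LessRay. Taking 2 or 3 for the SOC count, 5 in LessRay gives Fisher p of 0.42 or 0.70, which is not significant. With 10 in LessRay the smallest expected count is 12/2 = 6 or 13/2 = 6.5, so chi-square applies and p is 0.008 or 0.024.

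A 10-point tilt would therefore usually pass without a significant result, whereas one of 20 points or more would be a material source of false findings. The calculation shows what a tilt would do. It is not evidence that one exists.

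**The case against.** A reader might go further and infer that the word does mean different things in the two arms and does push the result towards LessRay. The documents do not support that.

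- **Meaning.** In the sequence of three, 'superior' can be read simply as the top grade. Nothing shows how these surgeons would take it. This stands, and limits the point to a risk.
- **Direction.** LessRay images come from a low-dose setting, and Background & Significance itself says that efforts to cut dose often degrade the image. A surgeon comparing with usual fluoroscopy could mark LessRay down, and an SOC surgeon can compare with other cases. This stands too. A tilt towards the device is plausible, not established.
- **Who is asked.** One might suppose that the question goes only to surgeons using the device. It goes to surgeons in both arms.
- **Reliance on one item.** The 1-10 rating has no comparative wording and is also compared, so the aim does not rest on the three-category item alone. This is a real but partial mitigation, because that rating is equally unmasked and unanchored.
- **Adequacy.** One might say that the survey cannot detect images too poor to operate with. 'Poor' and 'satisfactory' do carry an adequacy signal, and lost quality could show there. The phrase about not compromising quality voices a hope about the saved-image feature and operative time; it does not make this item the formal check on lower dose.
- **Size.** The shares in the illustration are assumed, and at a 10-point tilt a significant result would be uncommon.

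What survives is narrow: a comparative label without a reference, answered by surgeons who can see the arm, in a between-arm comparison for a stated aim. Whichever way it is read, the result would be hard to interpret, and the remedy is the same.

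**Conclusion.** The point holds as an avoidable measurement risk for the secondary image-quality aim. The top category lacks a reference, may be read differently by arm, and could bias the comparison, plausibly in favour of LessRay. Its size and direction cannot be taken from the documents. On the assumed base shares of 10% to 40%, a tilt of 20 points would yield a false positive for LessRay in about 34% to 41% of trials, and a tilt of 10 points in about 11% to 13%. These figures rest on one rating per case, truly equal images and a 'superior' versus other split.

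The primary radiation comparison and the 25-per-group sample size are unaffected. This is a cheap improvement to a secondary measure, not a flaw in the trial's main conclusion.

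**What to change.** Before enrolment:

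1. Replace the three answers with absolute, task-based categories that apply equally in both arms, for example 'inadequate for the surgical step', 'adequate' and 'excellent'.
2. Label the ends of the 1-10 scale in the same way, for example 1 = unusable and 10 = all landmarks clearly seen.
3. Instruct raters to judge the images on their own and not against another system.
4. State in the report that raters knew the arm.

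The cost is rewording one question, labelling one scale and adding one line of instruction. It needs no extra patients, staff, readers or procedures. The small downside is that surgeons who know the arm may still favour one system: the change removes the missing comparator, but preference among unmasked raters is reduced at most, not removed.

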A sample size of 25 per group achieves 93.7% power to reject the null hypothesis of equal means when the population mean difference is 500.0 with standard deviations of 650.0 for SOC group and 240.0 for DIE group. The significance level (alpha) of 0.050 is assumed using a two-sided two-sample unequal-variance t-test. Power calculations are based on historical data which demonstrated radiation doses of 1000 ± 650 in the SOC group and 373 ± 240 in the DIE group. The study would have approximately 80% power to show a 400 mRAD difference based on similar assumptions.

Subject Recruitment & Compensation:

Patients will be recruited from trauma population presenting to the Emergency Department who have sustained a closed hip fracture requiring intramedullary nailing.

There will be no compensation for participation in this study.

Consent Process:

Before a subject's participation in the clinical study, the investigator or study staff will be responsible for obtaining written informed consent from the subject after adequate explanation of the aims, methods, anticipated benefits, and potential hazards of the study and before any protocol-specific screening procedures or any investigational products are administered. Consent will take place in private patient rooms and patients and their families will have time to ask any questions and discuss privately. Inpatients will be given the option to keep the consent to consider participation up until their surgery is scheduled to take place.

Subject's Capacity to Give Legally Effective Consent:

Since there are no risks associated with use of the LessRay Device, LARs will be used for this study, since patients will be recruited from a trauma setting and may or may not be able to give legally effective consent.

Study Interventions:

There are no interventions performed in this study other than the normal operative fixation of the hip fracture. The LessRay Device is added to the regular C-Arm fluoroscopy machine.

Risk/Benefit Assessment:

There is no added risk to the patient. There is a theoretical benefit in less radiation exposure and decreased operative time.

Costs to the Subject:

There are no additional costs to the subjects as a result of participation in this study.

Data Analysis & Statistical Considerations:

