Data will be presented using standard summary statistics including the sample size, mean, standard deviation, median, inter-quartile range and range for continuous variables and counts with percentages for categorical data.

Radiation exposure and operative time will be compared between the DIE and SOC groups using either the t-test, if normally distributed, or Wilcoxon rank-sum test otherwise. Power calculations assume that the radiation exposure data are approximately normally distributed; however, this will be tested formally using the Kolmogorov-Smirnov test before comparing groups.

Percentages will be compared using the chi-square test or Fisher's exact test (expected cell counts < 5). Analyses will be done using SAS version 9.4 or higher and a $p < 0.05$ will be considered statistically significant.

Data & Safety Monitoring:

Data monitoring will be conducted on a routine basis by the PI and study team as specified below. Since this technology does not involve any risk to the patient other than loss of confidentiality, we do not anticipate any safety issues.

This study represents minimal risk to subjects, and no adverse events are anticipated. Accordingly, safety monitoring will be conducted to the extent that it ensures privacy and confidentiality, as indicated below.

Privacy, Data Storage & Confidentiality:

Any data that is stored in electronic format will be housed in a secure server behind the Duke University Medical Center firewall. Confidentiality of subject data will be ensured by de-identification of subject data. During data collection, subject identifiers and relevant data elements (specified in Section 3) will be recorded. Then, study-specific identification numbers will be assigned to each subject. Prior to dissemination of any

information in this database beyond the DUMC's secure servers or firewall, all identifiers will be stripped from the database and data will only be referenced by the study-specific identification numbers. A master log, which links the study-specific identification number to the study subject, will be generated in Excel. The master log will be stored as stated above, and will be accessible only to study staff. The adequacy of the Research Data Security Plan will be evaluated and approved by the Orthopaedic CRU prior to protocol conduct. Any publications or presentations that result from this research will not identify any subjects individually, and will present data in aggregate form only.

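### The primary surgeon's training level is collected to account for differences in dose and operating time, but no planned analysis uses it; the unit of analysis for two image ratings per case is also unstated

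*Combined protocol and SAP*

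**What the plan says.** Patients, not surgeons, are randomised between standard fluoroscopy (SOC) and the enhanced images (DIE) (Selection of Subjects).

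- **Operator data.** Design & Procedures collects the primary surgeon's PGY in "order to account for any differences in training level leading to increased OR time and/or radiation usage".
- **Dose and operating time.** Data Analysis & Statistical Considerations states: "Radiation exposure and operative time will be compared between the DIE and SOC groups using either the t-test", with the Wilcoxon rank-sum test if normality is rejected. It names no covariate.
- **Image quality.** Under Design & Procedures, "a brief survey will be issued to the primary and assistant surgeons asking the question" whether quality was poor, satisfactory or superior, plus a score from 1 to 10. Responses are to be compared between arms. The only test that fits the three-category item is the general statement that "Percentages will be compared using the chi-square test" or Fisher's exact test. No test is named for the 1 to 10 score.
- **Sample size (under Selection of Subjects).** "A sample size of 25 per group achieves 93.7% power to reject the null hypothesis of equal means". The inputs are a difference of 500 between the arm means, SDs of 650 (SOC) and 240 (DIE), and a two-sided Welch test at the 5% level. For a smaller effect the protocol claims "approximately 80% power to show a 400 mRAD difference based on similar assumptions".

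**The concern.** The protocol itself names the operator's training as a source of variation in both outcomes and says that it collects PGY for that reason. The analysis section then leaves that variation in the error term. With 25 patients per arm, precision is worth recovering, above all at the 400 mRAD difference, where the protocol claims only about 80% power. If the adjustment is left to be decided after the data are seen, an adjusted result will also carry less weight.

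The ratings raise a separate question. Fifty cases with two raters give up to 100 responses, and two people judging the same images will tend to agree. Chi-square and Fisher tests assume independent responses. The plan does not say whether the unit is the case, the rater role or the single response.

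**Working it through.** **1. The plan's own power.** Inputs from the sample-size paragraph: n = 25 per arm, SDs 650 and 240, two-sided alpha 0.05, unequal-variance t-test.

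SE = sqrt(650²/25 + 240²/25) = sqrt(16,900 + 2,304) = 138.58; Satterthwaite df = 30.4.

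- Difference 500: noncentrality 500/138.58 = 3.61, power 93.7%.
- Difference 400: noncentrality 400/138.58 = 2.89, power 79.8%.

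Both stated figures reproduce.

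**2. Are the unadjusted tests valid if surgeons differ?** Simulation of 50 individually randomised cases spread over 5 or 10 surgeons, with a surgeon intraclass correlation (ICC) from 0 to 0.5, gave type I error of 4.6% to 5.4% for the unadjusted comparison. There is no inflation.

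**3. What adjustment for PGY recovers.** Assumed scenario, built on the protocol's figures: means 1000 and 600 (the 400 difference), coefficient of variation 650/1000 = 0.65 in both arms, log scale.

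- SD of log dose = sqrt(ln(1 + 0.65²)) = 0.594.
- Effect = ln(1000/600) = 0.511.
- SE = 0.594 × sqrt(2/25) = 0.168; noncentrality = 3.04; with 48 df, unadjusted power = 84.6%.

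If PGY enters as one term and explains a share R² of the variance, the noncentrality becomes 3.04 / sqrt((1 − R²) × 47/46) with 47 df. The factor 47/46 is the average cost of chance imbalance in PGY between arms, (n − 3)/(n − 4) with n = 50.

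| R² (assumed) | Adjusted power | Change from 84.6% |
|---|---|---|
| 0 | 83.8% | −0.8 points |
| 10% | 87.4% | +2.8 |
| 20% | 90.9% | +6.3 |
| 30% | 94.1% | +9.5 |

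Simulation of the same model agreed to within half a point, with type I error about 5%.

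On the raw scale with the protocol's SDs, ideal adjustment (SDs multiplied by sqrt(1 − R²), no allowance for imbalance) at R² of 10%, 20% and 30% gives 83.8%, 87.8% and 91.6% at a difference of 400. At 500 it gives 95.7%, 97.4% and 98.7%. The equivalent unadjusted size is 25/(1 − R²), or about 28, 31 and 36 per arm.

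**4. Two ratings per case, if pooled.** Three-category ratings were simulated from a latent normal score with no arm effect, 50 cases and two raters, and 100 responses entered one chi-square test:

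| Within-case correlation (assumed) | Type I error, pooled chi-square |
|---|---|
| 0 | 4.9% |
| 0.3 | 6.9% |
| 0.5 | 9.4% |
| 0.7 | 12.0% |

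A t-test on the mean 1 to 10 score per case held 4.6% to 5.3% throughout.

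**The case against.** The strongest reply is that nothing here is an error. Under individual randomisation the two-group tests control type I error, their standard errors are correct for the unadjusted estimate, and the sample size was set for exactly such a test using total SDs. At the 500 difference, power is already 93.7%. Recording PGY could also serve only to describe the arms. All of this stands except the last point: the stated purpose is to account for training level, and a descriptive table does not do that.

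A reader might infer three stronger things that the documents do not support.

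- *That clustering by surgeon invalidates the dose and time results, or that the trial is underpowered.* Steps 1 and 2 contradict this.
- *That both ratings will be analysed as independent observations.* The text never says so. Comparing primary and assistant ratings separately fits it equally well and has no within-case inflation. The 7% to 12% is therefore a risk left open by silence, and it touches a secondary aim.
- *That a surgeon-level mixed model is needed.* The documents give no number of surgeons, no ICC and no statement that a surgeon operates on several cases. In the log-scale scenario, a surgeon random intercept raised power from about 86% to 93% with 5 surgeons and ICC 0.3, the most favourable setting tried. With 20 to 30 surgeons and ICC 0.2 the gain was only 2 to 3 points. Surgeon fixed effects can lose power: in a raw-scale simulation at a difference of 400, it fell from 82% to 77% with 10 surgeons and ICC 0.1.

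**Conclusion.** The point holds as a mismatch between the stated purpose of collecting PGY and an analysis section that does not use it. The cost is forgone precision, not bias, false positives or a wrong sample size. From a base of about 84% power, adjustment costs under one point if PGY is irrelevant and gains about 3, 6 or 10 points if it explains 10%, 20% or 30% of the variance. Those shares are assumptions, as the documents give no figure for them. The gains also assume that PGY enters as a single term with a roughly linear effect on log dose. The gain is smaller where power is already high, as at the 500 difference. The calculation is for dose; for operating time the documents give no SD, so only the direction carries over.

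The second, smaller point is that the unit of analysis for image ratings must be stated. The size of that risk depends on pooling, which is not specified, and on an unknown agreement between the two raters.

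**What to change.** In Data Analysis & Statistical Considerations:

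1. **Main comparison.** Analyse radiation dose and operating time with a linear model containing arm and primary-surgeon PGY. State in advance how PGY enters (one numeric term or a few groups) and how a primary surgeon beyond training is coded.
2. **Scale.** Fix it now, not after looking at residuals. The historical coefficients of variation are nearly equal (650/1000 = 0.65; 240/373 = 0.64), which favours the log scale for dose. If the log scale is chosen, say that the result is a ratio of doses and no longer a mean difference. If the raw scale is kept, allow a separate residual variance per arm, since the SDs are 650 and 240.
3. **Sensitivity analysis.** Keep the t-test or Wilcoxon test here.
4. **Optional.** Record a coded primary-surgeon ID, and add a surgeon random intercept if surgeons turn out to operate on several cases. Avoid surgeon fixed effects.
5. **Ratings.** Use the primary surgeon's rating as the one rating per case, or fit a model clustered by case. State that the two ratings are not pooled as independent, and name a test for the 1 to 10 score.

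The cost is a few sentences, one standard SAS procedure and, if step 4 is taken, one coded field. No extra patients are needed. The downside is small: the main result becomes a model-based estimate, with a loss of under one power point if PGY explains nothing.

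### Apart from a subjective surgeon survey and operative time, no imaging-failure events or operative harms are recorded by arm, because safety monitoring is limited to confidentiality

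*Combined protocol and SAP*

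**What the plan says.** On image quality, Background & Significance states a general trade-off: "Efforts to reduce the amount of radiation during fluoroscopic procedures often result in decreased image quality". It then says that the device works "using a low-dose pulse setting allowing for reduction in radiation dose while maintaining image quality". Purpose of the Study makes image quality something to be tested: "Secondarily, to evaluate whether the image quality and reproducibility of desired images can be improved with use of the LessRay Device".

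On risk, three places are absolute:
- Subject's Capacity to Give Legally Effective Consent: "Since there are no risks associated with use of the LessRay Device". This is given as the reason for using legally authorised representatives.
- Risk/Benefit Assessment: "There is no added risk to the patient".
- Data & Safety Monitoring: "Since this technology does not involve any risk to the patient other than loss of confidentiality, we do not anticipate any safety issues".

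The last section then calls the study one of minimal risk, expects no adverse events, and concludes that "safety monitoring will be conducted to the extent that it ensures privacy and confidentiality".

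On data, Design & Procedures lists demographics, fracture type, surgeon training level, C-arm emission, badge doses and operative time. It adds that "a brief survey will be issued to the primary and assistant surgeons", with a three-category rating and a 1 to 10 score, and says that the responses will be compared between standard of care (SOC) and DIE.

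**The concern.** The protocol uses the expectation that nothing will go wrong as its reason not to look. That expectation rests on the device offsetting the loss of image quality at low dose, and how image quality fares is part of what the trial sets out to learn. Background & Significance also says that the surgeon uses these images to check the reduction during the case, so inadequate imaging could bear on the operation itself.

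The trial exists to support a claim of less radiation without loss of image quality. Followed as written, it would measure the gain precisely but hold no event-level record of the possible cost: no count of cases in which DIE imaging was given up, and none of operative complications or reoperations. Its own statement of no added risk would be untested. A small dose difference would also be harder to explain, because a device that saves little dose could not be told apart from one that was often set aside.

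**Working it through.** **1. What is recorded, item by item**

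| Item | Recorded by arm? | Where |
|---|---|---|
| Patient and staff dose, C-arm emission | Yes | Design & Procedures |
| Operative time | Yes, with a test | Design & Procedures; Data Analysis & Statistical Considerations |
| Surgeon's opinion of image quality | Yes, subjective, no masking described | Design & Procedures |
| DIE abandoned, switched or malfunctioning | No | – |
| Intraoperative complications | No | – |
| Reoperation or any adverse event | No | – |

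The chi-square or Fisher rule in the analysis section can cover the three survey categories. No method is named for the 1 to 10 score. A poor rating is a crude sign of inadequate imaging, but it does not show whether DIE was abandoned or whether the patient was affected.

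**2. The number of patients available**

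The sample-size paragraph under Selection of Subjects gives 25 per group, SDs of 650 and 240, and a two-sided unequal-variance t-test at 0.05.
- Standard error: √(650²/25 + 240²/25) = √(16,900 + 2,304) = 138.6.
- Satterthwaite df: 19,204² / (16,900²/24 + 2,304²/24) = 30.4.
- Noncentral-t power is 93.7% for a difference of 500 (plan: 93.7%) and 79.8% for 400 (plan: about 80%).

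The plan's figures reproduce. This point does not depend on them; they only fix n = 25 per arm.

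**3. What 25 patients can say about an event if it is recorded**

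With no events seen, the exact upper bound is 1 − α^(1/n).
- One-sided 95%: 1 − 0.05^(1/25) = 1 − 0.887 = 11.3%.
- Upper limit of a two-sided 95% interval: 1 − 0.025^(1/25) = 1 − 0.863 = 13.7%.

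The chance of seeing at least one event in an arm is 1 − (1 − p)^25. The documents give no event rates, so these values of p are assumptions:

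| Assumed true rate | Chance of at least one event in 25 |
|---|---|
| 1% | 22% |
| 2% | 40% |
| 5% | 72% |
| 10% | 93% |

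**4. What a comparison between arms could show**

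Exact power of a two-sided Fisher test at 0.05 with 25 per arm, again on assumed rates, is about 20% for 5% versus 20% and about 82% for 5% versus 40%. Only a gross difference would be detected, so descriptive reporting is the right aim.

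**The case against.** The strongest case against has four parts.

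- **Imaging failures are not wholly unrecorded.** A reader might infer that the trial would hold no record of them at all. It would: the survey is compared by arm, and operative time is an indirect signal. This stands, and it confines the point to event-level data and operative harms.
- **The risk statements do not contradict the background.** A reader might infer a flat contradiction. The trade-off sentence concerns dose reduction in general, and the text goes on to say that the device maintains quality. It does not say that DIE images are worse or that patients could be harmed. This stands too. What remains is that an absolute statement of no risk is premature while image quality is under study. The safety section itself already says minimal risk, so the wording change is one of alignment.
- **The dose result would survive.** A reader might infer that unrecorded switches make it uninterpretable. The documents do not support that. The device is added to the regular C-arm, and emission and badge doses are taken for each case, so exposure after a switch on that machine should still count. If patients are compared by assigned arm, which the protocol does not state, switching would tend to dilute the difference. Only the explanation of a small difference suffers.
- **The gain is modest.** The added counts could not prove safety, and a decision to abandon DIE is made by the same surgeons who complete the survey. Both are true. A count with an interval is still more informative than no count, and it costs little.

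Revision of the reduction during surgery should not be counted as a harm. Checking reductions throughout the case is an intended use of the images, so a revision may mean that the imaging worked.

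**Conclusion.** The point holds as a limited gap that is cheap to close. The restriction on safety monitoring is a stated rule, not a detail left for later, and under it neither arm of 25 would yield any count of intraoperative complications or reoperations, nor the DIE arm any count of abandoned imaging. The dose comparison is not invalidated.

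Recording these events would let the trial report a count and an exact interval, with a one-sided 95% upper bound of 11.3% if none occurred among 25. It would not establish safety, and the report should say so.

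The bound assumes that all 25 patients in the arm contribute. That the operators know the arm is an inference from the absence of any described masking. The detection and power figures rest on assumed event rates.

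**What to change.** In Data & Safety Monitoring, replace the limit to privacy and confidentiality with a short list of recorded events:

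- **DIE arm only:** DIE imaging abandoned or switched to standard imaging (yes/no, with the reason). This cannot occur under SOC, so report it as a single-arm proportion. Take it from one added line on the existing surgeon survey or from the operative note; the protocol does not say what operative notes contain, so the survey line is the safer source.
- **Both arms:** intraoperative complication (yes/no, with description) and unplanned return to the operating room before discharge (yes/no), from the existing chart.

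In Data Analysis & Statistical Considerations, add that these counts will be reported by randomised arm with exact confidence intervals, as descriptive results, and that 25 per arm cannot establish safety.

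Align the absolute statements in the consent-capacity section, Risk/Benefit Assessment and Data & Safety Monitoring with the minimal-risk wording already in the last of these.

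The cost is a wording change, three yes/no fields and slightly more data abstraction. No extra imaging, readers, visits or patients are needed, and the dose analysis does not change.
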